**Specific Aim 2: To determine the safety profile of IV L-arginine in the treatment of acute VOE in children with SCD.**

Analysis of safety outcomes (acute chest syndrome, requirement of blood transfusion, oxygen use, return visits, and clinical deterioration) will be conducted using Mantel-Haenszel chi-square tests, stratified by clinical center and age group.

Summaries of incidence rates (frequencies and percentages), intensity, and relationship to study of individual Adverse Events (AEs) by System Organ Class and Preferred Term (MedDRA) will be prepared. All AEs beginning after randomization through 14 days or until hospital discharge (whichever comes first) will be included. ED revisits and hospital admissions will be tracked through day 28 after hospital discharge. The occurrence of any adverse event will be considered as a dichotomous outcome and will be compared between groups using a Mantel-Haenszel test, stratified by clinical center and age group. Adverse events will be coded using the latest version of the Medical Dictionary for Regulatory Activities (MedDRA).

**Specific Aim 3: (Exploratory) 3a. To characterize alterations in the arginine metabolome and mitochondrial function in children with SCD and VOE, and evaluate how it is impacted by IV arginine therapy.**

Arginine mechanisms of action are multifactorial and elusive in VOE, which is why incorporating an exploratory mechanism aim is important. However, it likely involves NO (Fig 1-2). SCD patients have an arginine deficiency that acutely worsens during VOE that should be assessed and treated. The benefit of arginine therapy may be in part- by simply replenishing a deficient nutrient. It was found that children are metabolically different during VOE compared to baseline with respect to the “arginine metabolome”, which includes amino acids that are precursors to (i.e. glutamine) or byproducts of arginine metabolic pathways (ornithine, citrulline, polyamines etc.). Hemolysis releases erythrocyte-arginase, which contributes to arginine consumption (Fig 1). This showed that the degree of arginine deficiency correlates with pain severity and need for hospitalization. It is essential from a mechanistic perspective to measure arginine levels in an arginine RCT pre and post-treatment. If arginine is working as a “drug”, there may be effects for all patients. However if we are merely treating an acute nutritional deficiency that has consequences (i.e. vaso-occlusion), the most robust response may occur in patients who have the greatest deficiency. Arginine bioavailability and the GABR will be determined pre and post treatment. GABR is associated with SCD complications and mortality risk, while others demonstrate a link to mortality risk and adverse events in cardiovascular disease and malaria. This mechanistic aim will determine whether GABR reflects an objective biomarker of pain severity, or one that identifies patients most likely to positively respond to arginine therapy. Subgroup analyses of clinical outcomes will be performed in patients from each tertile of GABR. Finding novel biomarkers that identify subgroup responders to drug therapies is an FDA and American Society of Hematology priority recently discussed at the SCD Clinical Endpoints Workshop. It was also demonstrated that IV arginine therapy increases mitochondrial activity (Fig 3). This proposal offers an opportunity to study the impact of arginine on mitochondrial function in a placebo-controlled fashion, necessary to assign causality. Improved mitochondrial function may be associated with decreased oxidative stress, a concept supported by our pilot data showing decreased protein carbonyls levels. Arginine is already used clinically in mitochondrial disorders, this would be an important novel mechanism of arginine in SCD to elucidate further, could lead to a new area of research and is easy to measure. Blood (for plasma, erythrocytes and platelets) will be drawn, processed and stored for future batched analyses at the time of presentation prior to study drug delivery (day 0), on day 1 and prior to discharge (or ED discharge, whichever comes first). The study will analyze the correlation between GABR and pain scores/opioid use, and the impact of IV arginine therapy on GABR compared to the placebo will be determined. Platelet mitochondrial respiratory complex activities will be measured as an indicator of mitochondrial function and aconitase activity as an index of mitochondrial oxidative damage.

**3b. This aim will establish a large SCD-VOE biorepository to explore future mechanistic studies.** Currently a biorepository of pediatric SCD-VOE samples does not exist. Acute pain samples are challenging to acquire given the unpredictable nature of ED visits. Blood is already being collected in this protocol to measure GABR and mitochondrial

function; storing addition samples adds significant value to the proposal at minimal cost, to answer future mechanistic questions. Additional analyses may be of interest (like arginase, ADMA, NOx, creatine etc.), but would require additional funding. This project would create the largest biorepository of SCD/VOE samples in existence; it would be a missed opportunity to not bank additional sample for future mechanistic studies given the effort of evaluating 360 children with SCD and VOE as part of this protocol.

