### 1.3 Hypotheses

The hypotheses of this study are:

1. Arginine therapy will decrease time-to-crisis resolution in children with an acute sickle cell vaso-occlusive pain episode compared to placebo.
2. Arginine therapy will lower total parenteral opioid use (mg/kg) compared to placebo.
3. Arginine therapy will improve pain scores compared to placebo.
4. Arginine will have a similar safety profile as placebo.
5. Arginine therapy will improve global arginine bioavailability and mitochondrial activity.

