## 5 Data Analysis

All analyses will be undertaken by the intention-to-treat (ITT) principle. Patients who drop out (discontinue study drug) will be followed and included in the ITT analysis. All statistical tests of hypotheses will be two-sided.

The hypotheses of this study are:

1. Arginine therapy will decrease time-to-crisis resolution in children with an acute sickle cell vaso-occlusive pain episode compared to placebo.

2. Arginine therapy will lower total parenteral opioid use (mg/kg) compared to placebo.
3. Arginine therapy will improve pain scores compared to placebo.
4. Arginine will have similar safety profile than placebo.
5. Arginine therapy will improve global arginine bioavailability and mitochondrial activity.

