## 5.1 Specific Aim Analyses

**Specific Aim 1: To determine the efficacy of IV L-arginine, when added to standard therapy, on the time-to-crisis resolution in children with SCD and VOE compared to placebo.**

The primary outcome (time-to-crisis resolution) will be analyzed by a Van Elteren test, stratified by clinical center and age group. The significance level for the primary comparison will be set at 0.05. The total length of stay in the hospital will also be analyzed, and this is expected to show the same result as the analysis of the primary outcome.

In addition to the assessment of the statistical significance of the treatment effect, the distribution of the primary outcome in each treatment arm using standard summary measures and an estimated difference in means between the two arms with a two-sided 95% confidence interval will be described.

The overall significance level for statistical tests on the secondary outcomes will be set at 0.05. Holms method will be used to adjust for multiple comparisons. The numeric secondary outcomes (opioid use, change in pain, and PRO measures) will be analyzed in the same manner as the primary outcome.

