## 5.2 Sample Size Calculations and Statistical Power

Based on a previous small trial, the difference between arginine and placebo groups is approximately 0.7 days (length of stay, which parallels time to crisis resolution). A Type I error bound of 0.05 (alpha) for the primary hypothesis will be used and it will be assumed that age is not informative of outcome (a conservative bound for sample size). A simulation-based approach is used to determine the sample size required to detect a difference (shift in distribution) of 0.7 days with 85% power. In order to simulate placebo outcomes, time-to-crisis resolution data from the MAGiC trial (both arms combined, as the treatment effect did not reach statistical significance) was used. For the arginine arm, outcomes were simulated from the same distribution, shifted down by 0.7 days. 5,000 trials were simulated. This process resulted in a required sample size of 166 per arm. Accounting for withdrawal (~1%), interim efficacy monitoring (inflation of 2%), and crossover/non-adherence (3%, for example, arginine subjects who do not receive a sufficient amount of study drug) results in an overall inflation of about 8% or a total of 180 per arm. Prior to the first interim analysis (after approximately 100 subjects), the DCC and CCC principal investigators, along with the DSMB, will review, blinded to by-treatment results, summaries of the outcome distribution (mean, median, IQR with both arms combined – to compare with MAGiC data), withdrawal rate, and non-adherence rates and may adjust the target sample size accordingly, as funding allows.

Given a total sample size of 180 per arm, the effect size that will be detectable in subgroup analyses of the primary outcome, for example, a differential treatment effect based on gender or hydroxyurea use will also be reported. With 85% power, it will be possible to detect an effect size (difference in differences) of about 1.3 days, or approximately 1.9 times the main treatment effect size for which the study is powered. With 80% power, it will be possible to detect an effect size of 1.2, or 1.7 times the main treatment effect size.

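### Hypothesis 4 expects similar safety, but the planned safety comparisons only test for a difference, with no effect estimate, interval or margin

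*Combined protocol and SAP*

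**What the plan says.** The safety hypothesis appears twice. Section 1.3 has "Arginine will have a similar safety profile as placebo" and section 5 has "Arginine will have similar safety profile than placebo". Neither place defines similar.

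The analysis is in section 5.1 under Specific Aim 2. For acute chest syndrome, transfusion, oxygen use, return visits and clinical deterioration, the analyses "will be conducted using Mantel-Haenszel chi-square tests, stratified by clinical center and age group". The occurrence of any adverse event "will be compared between groups using a Mantel-Haenszel test, stratified by clinical center and age group". Section 5 adds that "All statistical tests of hypotheses will be two-sided". Individual adverse events are summarised by frequency, percentage, intensity and relationship.

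The primary outcome is treated differently. Its test is accompanied by a commitment that "an estimated difference in means between the two arms with a two-sided 95% confidence interval will be described", and section 5.1 carries the same approach to the numeric secondary outcomes. No such commitment is made for the safety outcomes.

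On error rates, section 5.1 says "The significance level for the primary comparison will be set at 0.05" and sets an overall 0.05 for the secondary outcomes. It states no level for safety. The sample size in section 5.2 is chosen "to detect a difference (shift in distribution) of 0.7 days with 85% power", which concerns the primary outcome only; no power is given for any safety outcome.

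**The concern.** A Mantel-Haenszel test takes no difference as its null hypothesis. Rejecting it is evidence of a difference. Failing to reject it is evidence of nothing in particular unless one also knows how large a difference the data rule out. A hypothesis of similarity needs that second piece of information, and the plan does not produce it.

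The abstract presents the trial as a source of data for regulatory approval, and safety is one of its two main aims. If the safety results are reported as planned, a reader would have a set of p-values and adverse event tables but no statement of how much excess harm the trial has excluded. For less common outcomes, a non-significant p-value would be compatible with a substantial excess.

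**Working it through.** **Inputs.**
- Size: 180 per arm (section 5.2), equal allocation (section 4.2).
- Strata: 10 sites (section 1.1) by 2 age groups (section 4.2), so 20.
- Test: two-sided (section 5). A level of 0.05 is assumed, since none is stated for safety.
- Event rates: section 2.8 gives a 72-hour re-hospitalization rate of 6% in phase 2 safety data on 83 children, not reported by arm, and 20% from the literature. The plan gives no expected rate for the other safety outcomes. A range of 3% to 20% in the placebo arm is therefore assumed.

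**The plan's own figure.** 166 × 1.08 = 179.3, which rounds up to the stated 180 per arm. There is no safety power figure to reproduce.

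**Power to detect a doubling.** With placebo rate p₁, arginine rate p₂ = 2p₁ and p̄ = (p₁ + p₂)/2:

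power = Φ{[(p₂ − p₁) − 1.96 √(2p̄(1 − p̄)/n)] / √[(p₁(1 − p₁) + p₂(1 − p₂))/n]}

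For 6% against 12%, p̄ = 0.09:
- null standard error = √(2 × 0.09 × 0.91/180) = 0.0302, and 1.96 × 0.0302 = 0.0591
- alternative standard error = √[(0.0564 + 0.1056)/180] = 0.0300
- power = Φ[(0.0600 − 0.0591)/0.0300] = Φ(0.03) = 51%

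**Check with the planned test.** The stratified Mantel-Haenszel test was simulated 20,000 times per scenario, with 20 strata of uneven assumed sizes and no continuity correction. Its rejection rate with equal arms was 4.6% to 4.9%.

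**Precision.** If both arms show rate p, the half-width of the 95% CI for the risk difference is 1.96 √(2p(1 − p)/n). At 6%: 1.96 × √(2 × 0.06 × 0.94/180) = 4.9 points.

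| Placebo → arginine | Power, formula | Power, simulated test | Half-width at the placebo rate |
|---|---|---|---|
| 3% → 6% | 28% | 27% | 3.5 points |
| 5% → 10% | 44% | 44% | 4.5 points |
| 6% → 12% | 51% | 51% | 4.9 points |
| 10% → 20% | 76% | 76% | 6.2 points |
| 15% → 30% | 93% | 93% | 7.4 points |
| 20% → 40% | 99% | 99% | 8.3 points |

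With a continuity correction, simulated power is lower: 36% at 5%, 45% at 6% and 71% at 10%. The smallest risk ratio detectable with 80% power is 2.7 at 5%, 2.5 at 6%, 2.06 at 10% and 1.65 at 20%. Detecting 6% against 12% with 80% power would need 356 per arm.

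**What an interval would show.** If both arms showed 6% (10.8 events per arm on average), the risk difference would be 0 ± 4.9 points, while the risk ratio interval would be 0.44 to 2.27. At 10% the ratio interval would be 0.54 to 1.86, and at 20% it would be 0.66 to 1.51. The planned p-value conveys none of this.

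**The case against.** The strongest reply is that hypothesis 4 is a one-line expectation, not a formal claim. Aim 2 is worded as determining a safety profile, no alpha or power is attached to it, and the trial is sized on efficacy. Safety is also not judged by the tests alone: adverse events are tabulated, a medical monitor assesses every serious event (section 8.2.6), and the DSMB reviews all adverse events at its scheduled meetings.

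This disposes of some stronger readings that a reader might be tempted by:

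- *That the plan will treat a non-significant test as proof of similarity.* No text says so. The inference is understandable, because no other criterion is offered and sections 2.8 and 2.9 call earlier safety rates similar without a margin. It remains an inference.
- *That a clinically relevant excess would be hidden.* The tabulation and independent review make that too strong.
- *That a doubling of any safety event is easily missed.* At 15% to 20% it would be detected with 93% to 99% power. The documents give 20% for re-hospitalization alongside 6%, and any adverse event may well be common.
- *That 6% is the placebo rate.* Section 2.8 does not report it by arm.

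Two further objections concern the remedy. An interval adds no power. And the choice of scale matters: equal observed rates of 6% exclude a 6-point excess on the difference scale but not a doubling on the ratio scale. Both are true. They are reasons to fix the scale in advance and to report the interval, since it shows what the trial has and has not excluded.

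What none of this answers is the mismatch itself. Tabulation and DSMB review protect participants, but they do not supply a between-arm estimate with its uncertainty, and section 5.1 does not explicitly promise even percentages by arm for the five named outcomes.

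**Conclusion.** The point holds as a mismatch between hypothesis and analysis. Hypothesis 4 asserts similarity; the only planned between-arm safety comparisons are tests for a difference; and no estimate, interval, margin or other criterion is given. That conclusion depends on no assumed event rate.

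The practical size does depend on assumed rates. With 180 per arm and an assumed two-sided 0.05, a true doubling would go undetected in roughly half of trials at 5% to 6% (power 44% to 51%), in nearly three quarters at 3% (power 28%), and in about a quarter at 10% (power 76%). Above that the concern fades. It should be stated for outcomes with rates up to about 10%. Which of the named outcomes fall in that range cannot be settled from the documents, apart from 72-hour re-hospitalization, where the two figures given lie on either side of it.

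The primary result is unaffected. The safety conclusion is what needs firmer ground.

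**What to change.** In section 5.1, Specific Aim 2, for each named safety outcome and for any adverse event:

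1. Report the number and percentage with the event in each arm.
2. Beside the existing test, report the Mantel-Haenszel stratified risk difference with a 95% CI, using the same center and age strata. With 360/20 = 18 participants per stratum on average, specify a variance estimator that is valid for sparse strata.
3. Base the safety conclusion on the excess that the interval does and does not exclude, not on the p-value.

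In sections 1.3 and 5, reword hypothesis 4 as an aim to estimate the difference in safety event rates between arginine and placebo. With that wording no margin is required. If the claim of similarity is to stay, a margin has to be stated in advance.

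The cost is plan wording, slightly more output and a more cautious safety statement. No patients, data collection or trial conduct need to change, and the planned tests can remain.

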- c – Research labs: will be obtained with routine daily blood draws whenever possible and may be drawn on days when the research and clinical team suspect the patient may be discharged to avoid multiple venipunctures. In the event the patient is not discharged on that date, discharge labs should be drawn again prior to discharge. Baseline labs to be drawn before the start of study drug.
- d – Screening CMP from a clinically ordered CMP or the last CMP in the medical record within the last 12 months will be reviewed. If there are any values within higher than protocol defined cut offs for study drug withdrawal, then a CMP is to be drawn and reviewed prior to randomization. For participants with normal past CMP, a CMP will be done on day 2.
- e – Pregnancy test obtained at Pre-Dose for females 13 years and older.
- f – The first set of Vital Signs (including oxygen saturation) and Pain scores will be captured when the patient first presents to the Emergency Department. The highest and lowest pain scores will be recorded from Day 1 through Day 8 (or within 6 hours of Discharge). The first set of vitals signs after 6 am will be collected up until Day 8/Discharge, whichever comes first. Ensure oxygen saturation is captured at Pre-Dose and within 6 hours of Discharge.
- g – Symptoms Questionnaire will be completed daily through Day 14 or Discharge.
- h – Use of Parenteral Opioids will be documented every shift by nursing staff per standard protocol, including opioids delivered by the PCA device as well as any intravenous, intranasal and/or oral opioids used. Data on daily opioid use will be collected and recorded.
- i – AEs and SAEs will be monitored daily through discharge or through 14 days of hospitalization; Return ED visits and hospitalizations will be followed for 28 days after hospital discharge.
- j – Patients will be randomized within 12 hours of their initial dose of parenteral opioid in the ED or ward and Arginine will be administered TID.

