### 8.2.3 Time Period for Adverse Events

For purposes of this study, events that occur following randomization through 14 days after study drug initiation or until hospital discharge (whichever comes first) will be reported as adverse events. ED revisits and hospital admissions will be tracked through 28 days following hospital discharge. Specifically, events that occur following parental permission to participate in the study, but prior to actual randomization, are not adverse events. These should be recorded as baseline conditions.

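### Adverse event capture ends at discharge, which is expected sooner on arginine; supportive time-based analyses would make the yes/no comparison more interpretable

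*Combined protocol and SAP*

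**What the plan says.** In the combined protocol and SAP, three places close AE capture at discharge. Section 5.1 (Specific Aim 2): "All AEs beginning after randomization through 14 days or until hospital discharge (whichever comes first) will be included". Section 8.2.3 counts events "through 14 days after study drug initiation or until hospital discharge (whichever comes first) will be reported as adverse events". Table 3, note i, in section 4.5.1: "AEs and SAEs will be monitored daily through discharge or through 14 days of hospitalization".

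The between-arm analysis of AEs overall is in section 5.1: "The occurrence of any adverse event will be considered as a dichotomous outcome and will be compared between groups using a Mantel-Haenszel test", stratified by center and age group. AEs by MedDRA class and term, intensity and relationship are summarized as frequencies and percentages. Acute chest syndrome, transfusion, oxygen use, clinical deterioration and return visits have their own Mantel-Haenszel tests.

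After discharge, "ED revisits and hospital admissions will be tracked through day 28 after hospital discharge". Section 1.4 names 72-hour and 28-day return visits, and section 8.2.7 follows unresolved serious AEs.

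The plan expects arginine to shorten stay. Section 5.1 says of length of stay that "this is expected to show the same result as the analysis of the primary outcome", and section 5.2 that "the difference between arginine and placebo groups is approximately 0.7 days (length of stay, which parallels time to crisis resolution". Study drug also stops at discharge, or after 21 doses if that comes first (section 4.3.2).

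**The concern.** If arginine works as hypothesized, its patients leave sooner and are watched for AEs for less time. Observation time then depends on treatment, and no planned between-arm AE analysis takes account of it. A lower or equal AE percentage on arginine could mean fewer events per day, or only fewer days in which to record one.

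Hypothesis 4 (section 1.3) is that safety is similar, with no margin stated. Similar percentages may well be read as support for it: section 2.9 reports a shorter stay and similar AE rates in an earlier oral arginine trial and takes the AE rates as reassuring (that trial's AE window is not given). The primary analysis and DSMB review are not affected.

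**Working it through.** **Inputs from the documents**
- Difference in stay: 0.7 days (section 5.2). The 17-hour trend in section 2.8 agrees: 17/24 = 0.71 days.
- Sample size: 180 per arm (section 5.2). Check: 166 × 1.08 = 179.3, rounded up to 180.
- The documents state no figure for the AE comparison, so there is none to reproduce.

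**Assumptions (not in the documents)**
- Mean placebo stay T of 3, 4 or 5 days, either the same for every child or varying (gamma, shape 2). Each arginine stay is 0.7 days shorter, with a floor of 0.1 day and a cap of 14 days.
- Placebo risk r of any AE of 10%, 20% or 40%.
- AE timing either constant or clustered early (time constant 1 day).
- One time zero, ignoring any gap between randomization and first dose.

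**Model.** P(any AE) = 1 − exp(−k·G(T)), with G(T) = T (constant) or G(T) = 1 − exp(−T) (early). Set k so that the placebo risk is r, then apply the same k to the shorter arginine stay.

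**Example: T = 4, r = 20%, fixed stays, equal true hazards**
- Constant: k = −ln(0.8)/4 = 0.0558. Arginine risk = 1 − exp(−0.0558 × 3.3) = 16.8%, which is 3.2 points lower.
- Early: k = 0.2231/0.9817 = 0.2273. Arginine risk = 1 − exp(−0.2273 × 0.9631) = 19.7%, which is 0.3 points lower.

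**Shift in the arginine percentage when true hazards are equal** (ranges over T and over fixed or varying stays). The half-width is 1.96 × √(2r(1−r)/180).

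| Placebo risk | Constant: points lower | Early: points lower | 95% CI half-width |
|---|---|---|---|
| 10% | 1.3-2.2 | 0.1-1.5 | 6.2 |
| 20% | 2.5-4.3 | 0.1-3.0 | 8.3 |
| 40% | 4.5-8.1 | 0.2-5.7 | 10.1 |

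**Hazard ratio that equal percentages would hide.** With fixed stays it is G(T)/G(T − 0.7), whatever r is.

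| Stays | Constant | Early |
|---|---|---|
| Fixed, T = 3 / 4 / 5 | 1.30 / 1.21 / 1.16 | 1.06 / 1.02 / 1.01 |
| Varying | 1.17-1.41 | 1.09-1.23 |

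The 1.23 depends on very short stays: at a 3-day mean, about 10% of arginine children sit at the 0.1-day floor and 19% leave within 12 hours. Raising the floor to 12 hours lowers it to about 1.13.

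**What the added analyses can deliver**
- In simulation with discharge unrelated to AE risk, a Cox model censored at discharge recovers the true hazard ratio within 0.015.
- If sicker children both stay longer and have more AEs, the hazard ratio tilts against arginine when true hazards are equal: 1.02-1.07 under modest and 1.04-1.20 under stronger assumed shared severity. The crude risk ratio in the same scenarios is 0.82-0.99, so the two err in opposite directions.
- Precision: the 95% CI factor is exp(1.96 × √(4/d)) with d = 360r = 36, 72 or 144 first events, giving 1.92, 1.59 and 1.39.
- An early window with discharge as a competing event leaves no shift with fixed stays, but up to 3.7 points at 24 hours and 5.2 points at 48 hours with varying stays.

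**The case against.** Five points on the other side deserve weight.

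1. The planned test is sound for its own question. Risk per treatment course, by intention to treat, is a legitimate safety comparison, and fewer days at risk is part of what arginine would do. A reader might infer that the test is invalid or its type I error inflated. The documents do not support that: dosing ends at discharge too, so AE risk over the stay would truly differ. This stands, and the test should stay.

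2. Existing coverage is wider than one yes/no result. Length of stay is analyzed, so a difference in observation time will be visible. Return visits and follow-up of unresolved serious AEs cover much of the time after discharge. A reader might infer that post-discharge harm goes unseen; what is missed is new events that bring no return visit. This context is useful but does not relate AEs to time observed.

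3. The 16-41% figure is the less supported scenario for drug-attributable events. Section 8.2.2 lists reactions such as flushing, vomiting and warmth at the infusion site, and the loading dose comes first (section 4.3.2); both point to early clustering. Disease complications may follow another pattern. This stands, so the early range should lead.

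4. The additions are imprecise and carry biases of their own. With an assumed 4-day stay, 40% risk and a true hazard ratio of 1.27, a first-AE rate ratio has only about 31% power. This stands and limits them to a descriptive role.

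5. Starting the clock at first dose would omit AEs between randomization and dosing and leave undosed children with no time origin, contrary to section 5. This also stands, so the origin should be randomization.

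**Conclusion.** The point holds as an inexpensive improvement to the safety analysis. AE observation time is expected to depend on treatment, and no planned between-arm AE analysis accounts for it.

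The plausible hidden excess in daily AE rate runs from about 1-6% (early clustering, fixed stays), through an upper end of 13-23% (early clustering, widely varying stays), to 16-41% (constant hazard). All of these rest on assumed stays, AE risks and timing, and on a 0.7-day difference that is itself a design assumption drawn from a small trial in which it was only a trend. Every computed shift in percentage is smaller than the sampling uncertainty of the risk difference.

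A reader might conclude that the trial will conceal a safety signal, or that the added analyses would settle the matter. Neither follows. The documents do not show that any excess exists, and discharge is probably informative, so the additions make the result more interpretable without fully resolving it.

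**What to change.** Keep the Mantel-Haenszel test. In section 5.1 (Specific Aim 2), pre-specify as supportive and descriptive:

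- (a) Time to first AE from randomization in all randomized patients, stratified by center and age group, censored at discharge or day 14, with hazard ratio and 95% CI.
- (b) Cumulative incidence of first AE by a short fixed time from randomization, for example 24 and 48 hours, or study days 1 and 2 where only the onset date is recorded. Treat discharge as a competing event and show the share of each arm already discharged.
- (c) A version from first dose as a sensitivity analysis.

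Apply the same to acute chest syndrome and transfusion where they are ascertained only in hospital. Report all of this beside length of stay and the 72-hour and 28-day return visits.

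The cost is SAP wording and a few tables. Onset date, and time where appropriate, are already recorded (section 8.2), and Table 3, note g, adds that the "Symptoms Questionnaire will be completed daily through Day 14 or Discharge". Some timing will therefore be known only to the day, which is coarser than the 0.7-day difference at issue. The other downsides are a hazard ratio that may tilt against arginine (about 1.02-1.20) and is imprecise (95% CI factor about 1.4-1.9), and AEs after discharge without a return visit, which remain unrecovered.
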